Precision medicine is an emerging medical model that customizes healthcare decisions based on an individual patient's characteristics, aimed at delivering the right treatment at the right time.² A population approach to precision medicine takes into account environmental exposures.³ As emphasized in the Scientific Report of the 2015 *Dietary Guidelines for Americans*,⁴ multiple determinants of health from an individual's physical and socio-emotional characteristics to the environment in which they live influence treatment adherence and efficacy. The "Exercise is Medicine" initiative calls for healthcare providers to prescribe physical activity for the prevention, treatment, and management of chronic diseases.⁵ An opportunity lies in leveraging precision medicine to create individualized physical activity plans for the prevention and treatment of obesity, a disease affecting 23% of Louisiana's children. To determine optimal, individually tailored exercise prescriptions, we must first identify the contexts within a child's day that facilitate physical activity and minimize time spent in sedentary pursuits, particularly among children with obesity. To achieve this aim, we will achieve the following objectives:

Objective 1: Determine the effect of severe obesity on physical activity, sedentary behavior, and cardiometabolic risk factors during childhood and adolescence and whether these associations are modified by race (NP 107, C4, PS 4A).

Hypothesis 1.A: Severe obesity will be associated with greater changes in physical activity, sedentary behavior, and cardiometabolic risk factors.

Hypothesis 1.B: Associations of severe obesity with physical activity, sedentary behavior, and cardiometabolic risk factors will be stronger among African American versus White youth.

Objective 2: Investigate the contribution of (total, regional, and depot-specific) fat accumulation on changes in physical activity, sedentary behavior, and cardiometabolic risk factors during childhood and adolescence (NP 107, C4, PS 4A).

Hypothesis 2: The accumulation of total, trunk, and visceral fat will be significantly associated with changes in physical activity, sedentary behavior, and cardiometabolic risk factors during childhood and adolescence.

Objective 3: Determine barriers and facilitators of physical activity that are related to obesity, including environmental and socio-emotional factors. (NP 107, C4, PS 4A).

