The hypotheses will be tested using a series of generalized linear models with severe obesity as the independent variable. First, linear mixed effect models will be used to test for effects between BMIz and each dependent continuous variable (change in: min/day sedentary behavior, min/day MVPA, and each cardiometabolic risk factor). Next, logistic regression models will be used to determine the association between BMIz with the likelihood of not meeting recommended behaviors (i.e. top quartile of min/day of sedentary behavior; MVPA < 60 min/day) or being at elevated cardiometabolic risk. Finally, the cohort will be stratified into two groups based on obesity at Year 0: severely obese (SO) and not severely obese (NSO). Logistic regression models will be used to determine associations between SO (vs. NSO) and each dependent variable (i.e. change in: minutes/day sedentary time, minutes/day MVPA, and each continuous cardiometabolic risk factor). Covariates will include age, sex, dietary intake, and race. School

term vs. school holiday will be considered as an additional covariate if time of year is significantly associated with the independent and dependent variables.

Secondary analysis will use MRI and DXA as covariates in the model (namely the visceral, trunk, and total body fat). These measurements, along with BMIz, may be highly correlated. Various variable select criteria (including LASSO and support vector machine) will be used to determine which combination of these variables best explains the variance in the data. The full model will enable the comparison of imaging-based body composition measures vs. BMIz alone and their associations with physical activity, sedentary behavior, and cardiometabolic risk factors in children.

As exploratory analyses, dietary intake will be tested as a potential mediator to explain significant associations between the predictor variable (BMIz) on outcomes (physical activity, sedentary behavior, and cardiometabolic risk factors). Series of sequential models will be used to test each pathway using a path analysis model based on the Baron and Kenny causal steps for mediation.73,74

Objective 2:

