Analyses to test Hypothesis 2 will be conducted using a series of linear regression models (i.e. linear mixed effects models). Based on difference score between Years 0 and 2 for total body fat, the group will be divided into two dichotomous groups using percentiles: high fat gainer (HFG) and low fat gainer (LFG). These variables will be used to predict changes in physical activity, sedentary behavior, and each cardiometabolic risk factor in linear mixed effect models. Covariates will include age, sex, dietary intake, and race. School term vs. school holiday will be considered as an additional covariate if time of year is significantly associated with the independent and dependent variables. Secondary analysis will use MRI and DXA as covariates in the model (namely the visceral, trunk, and total body fat). As previously reported, variable select criteria (including LASSO and support vector machine) will be used to determine which combination of these variables best explains the variance in the data. The full model will enable the comparison the accumulation of imaging-based body composition measures vs. BMIz alone and their associations with change in physical activity, sedentary behavior, and cardiometabolic risk factors in children. Finally, there are no standard accepted definitions of pediatric severe obesity to dichotomize participants based on MRI or DXA measures of body fat. Therefore, receiver operating characteristic curves will be created to estimate the value at which visceral, trunk, and body fat best correspond with the BMI definition of severe obesity (i.e. $BMI \ge 120\%$ of the 95th percentile1). Clinically relevant cut-points of severe obesity based on total, trunk, and visceral body fat will be established among this diverse cohort of adolescents.

Power analysis

Objective 1:

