Objective 2:

The primary outcome for the second objective is the relationship between total fat accumulation and change in sedentary behavior. Based on data from Berkey et al.,75 we estimate an overall change in sedentary behavior of 12 minutes/day increase in the HFG and 3.6 minutes/day increase in the LFG over a two-year period. **Table 6** shows sample sizes required to detect various differences for the change between groups. With a sample size of up to 345, this will provide at least 80% power for detecting a difference in the change between groups of 8.4 minutes/day, allowing for the anticipated 25% dropout. Therefore, with our sample size of up to 345 participants, we will have sufficient power to detect a difference between the HFG and LFG groups.

Change in minutes	Change in minutes	Change between	Standard deviation	Minimum sample	Total sample size
of sedentary time	of sedentary time	groups	of change between	size	(allows for 25%
for HFG	for LFG		groups		dropout)
12	2.4	9.6	24	194	259
12	3	9.0	24	220	293
12	3.6	8.4	24	255	Up to 345
12	4.2	7.8	24	292	389

Table 6. Difference in changes in sedentary time between the high fat vs. low fat gainer group. *Note.* HFG is the group classified as high fat gainers; LFG is the group classified as low fat gainers.

Secondary analyses based on the second objective will include modeling the relationship between fat mass accumulation and change in physical activity. Using data from Berkey et al.,75 we estimate an overall decrease of 19.2 minutes/day of MVPA in the HFG and a decrease of 4.8 minutes/day of MVPA in the LFG over a two-year period. With a sample size of up to 345 (including anticipated dropout), this will provide 93.4% power for detecting a difference in the change between groups of 14.4 minutes/day.

Contingencies

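### Hypothesis 2 names total, trunk and visceral fat gain, but only total fat gain has its own exposure and test; trunk and visceral fat are examined only conditionally, in a secondary joint analysis with no stated coefficient test

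*Combined protocol and SAP*

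**What the plan says.** Study Objectives, Hypothesis 2: "The accumulation of total, trunk, and visceral fat will be significantly associated with changes in physical activity, sedentary behavior, and cardiometabolic risk factors".

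Statistical Analysis, Objective 2, describes the test of that hypothesis. It forms high and low fat gainers: "Based on difference score between Years 0 and 2 for total body fat, the group will be divided into two dichotomous groups using percentiles". These two groups (HFG and LFG) then predict the outcome changes, adjusted for age, sex, dietary intake and race.

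The other depots appear in the next step: "Secondary analysis will use MRI and DXA as covariates in the model (namely the visceral, trunk, and total body fat". The plan continues that "variable select criteria (including LASSO and support vector machine) will be used to determine which combination of these variables best explains the variance", and then: "The full model will enable the comparison the accumulation of imaging-based body composition measures vs. BMIz alone and their associations with change". The parallel text under Objective 1 concedes of the same measures: "These measurements, along with BMIz, may be highly correlated".

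Power analysis, Objective 2, sets the hierarchy: "The primary outcome for the second objective is the relationship between total fat accumulation and change in sedentary behavior". Of the planned sample it says "this will provide at least 80% power for detecting a difference in the change between groups of 8.4 minutes/day", for the HFG/LFG contrast. No power figure, separate model or multiplicity rule is given for trunk or visceral fat. The ROC analysis in the same section relates the fat measures to BMI-defined severe obesity, not to the outcomes of Hypothesis 2.

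**The concern.** Two of the three exposures named in the hypothesis have no model of their own. Followed as written, the plan yields a test for total fat gain. For trunk and visceral fat it yields a selected subset of correlated terms, or coefficients from a joint model.

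A joint visceral coefficient asks whether visceral fat gain matters at fixed trunk and total fat gain. That is a legitimate question, but it differs from whether visceral fat gain is associated with the outcome at all. The DXA trunk measure is a regional part of the whole-body total, so some overlap is built in.

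Depot-specific accumulation is a main reason the Background gives for using MRI and part of the novelty it claims. The plan does not say what result would support or contradict that part of the hypothesis. A depot that is dropped or non-significant in the joint model could reflect shared variance rather than absence of association.

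**Working it through.** **1. The plan's own figure (Table 6, row 8.4).** Inputs from the plan: difference 12 − 3.6 = 8.4 min/day, SD 24, power 80%, dropout 25%. Assumed: two-sided alpha 0.05 (stated only under Objective 1) and a 1:1 split (the percentile is not stated).

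Total N = 4 × (1.960 + 0.842)² × 24² / 8.4² = 256.3, or 258 as two groups of 129. The plan states 255. With dropout, 258 / 0.75 = 344; the plan states up to 345.

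Power at 258: standard error = 24 × √(2/129) = 2.988; 8.4 / 2.988 = 2.811; Φ(2.811 − 1.960) = 80.3%. The total-fat figure reproduces. There is no trunk or visceral figure to reproduce.

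**2. Coverage of the hypothesis.**

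| Exposure in Hypothesis 2 | Own change-score exposure | Own power figure | Where it enters |
|---|---|---|---|
| Total fat gain | Yes (HFG/LFG) | Yes (Table 6) | Primary model |
| Trunk fat gain | No | No | Secondary covariate, selection, full model |
| Visceral fat gain | No | No | Secondary covariate, selection, full model |

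**3. Power of the joint coefficient.** The documents give no correlations, so two sets are assumed:
- high: total-trunk 0.95, total-visceral 0.75, trunk-visceral 0.80
- moderate: 0.85, 0.55, 0.60

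The diagonal of the inverse correlation matrix gives variance inflation factors (VIF) of 12.5 and 4.0 for trunk, and 2.8 and 1.6 for visceral (high and moderate).

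The true standardised effect is r = 0.174, about the size detectable with 80% power at n = 258: (1.960 + 0.842) / √258 = 0.174. All 258 children are assumed to have all three measures, with no other covariates.

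Noncentrality = r × √(n / VIF) / √(1 − r²), and power ≈ Φ(noncentrality − 1.960), plus a negligible opposite tail.

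| Truly related depot | VIF | Noncentrality | Power by formula | Power by simulation |
|---|---|---|---|---|
| Either, in its own model | 1 | 2.84 | 81% | about 80% |
| Visceral, joint, moderate | 1.58 | 2.26 | 62% | 60% |
| Visceral, joint, high | 2.79 | 1.70 | 40% | 39% |
| Trunk, joint, moderate | 3.96 | 1.43 | 30% | 28% |
| Trunk, joint, high | 12.5 | 0.80 | 13% | 12% |

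**4. Selection.** In a simulation with no true effects (250 runs per correlation set), ordinary regression after LASSO gave p < 0.05 for 21-31% of the terms that LASSO had selected. Each depot was selected in only 14-21% of runs, so these rates rest on few selections. The unconditional rate of being both selected and below 0.05 was 3-6% per depot. The defect is therefore in reading a selected term's p-value at face value. The plan names no post-selection method, and a support vector machine supplies no p-value.

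**5. What separate models cannot show.** If the effect acts only through total fat (r = 0.174), the marginal correlation of another depot is r times its correlation with total fat:
- visceral, moderate set: 0.174 × 0.55 = 0.096, detected alone in about 34% of trials
- trunk, high set: 0.174 × 0.95 = 0.165, detected alone in about 77% of trials

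Separate models test association, not depot specificity.

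**The case against.** The strongest reply is that the plan declares a hierarchy. Total fat and sedentary time are primary and powered; the depots are labelled secondary, in an observational cohort. Objective 2 speaks of the contribution of fat accumulation, and a joint model is a reasonable way to study contribution. The full-model sentence mentions accumulation of the imaging measures and their associations with change, so depot change scores may well be intended.

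Much of this stands. A reader might infer that trunk and visceral fat get no valid test at all. The documents do not support that: a full model fitted without selection keeps its nominal type I error of about 5%. What it lacks is a stated coefficient test, adequate power under collinearity, and an estimand matching the unconditional reading of the hypothesis. A reader might also infer that Objective 2 as a whole is compromised. It is not, because the primary contrast does not depend on this step.

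It is also tempting to ask for three separate models under one Holm correction. That would put the declared primary test at alpha 0.05/3 = 0.0167 in its first step: Φ(2.811 − 2.394) = 66.2% power instead of 80.3%. Separate models alone would also often credit a depot with a general adiposity effect, so the joint model has a proper place.

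What does not fall away is that a secondary label leaves the hypothesis naming three exposures, while the analysis defines an unconditional test for one.

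**Conclusion.** The gap is real and lies in the analysis text, not in the sample-size arithmetic. Trunk and visceral fat gain are named in Hypothesis 2 but are examined only conditionally on total fat, with selection and without a stated test.

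The illustrative cost is a fall from about 80% power in a depot's own model to 39-60% (visceral) or 12-28% (trunk) in the joint model. Those ranges rest on the assumed correlations, r = 0.174, complete measurements in 258 children, and no further covariates. The direction holds whenever the measures are correlated. The mismatch between hypothesis and analysis needs none of these assumptions.

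Severity is should-fix: the declared primary analysis of total fat and its stated 80% power are unaffected.

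**What to change.** - Keep the HFG/LFG total-fat contrast on change in sedentary time as the primary test at alpha 0.05.
- Add one prespecified model for Year 0 to Year 2 change in trunk fat and one for change in visceral fat, with the same covariates. Test them after total fat in a stated fixed order, or use Holm over these two only. State whether they are tested only if total fat is significant; if not, error across all three tests is not held at 0.05.
- Report the unselected joint model alongside, to show whether a depot adds to total fat.
- Label LASSO and support vector machine selection exploratory.

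The alternative is to narrow Hypothesis 2 to total fat and call trunk and visceral fat exploratory.

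The cost is wording and a few extra model runs on data already planned, with no change in enrolment for the primary test. The depot tests pay instead. If each depot had the same 8.4 and SD 24 (an assumption), the first Holm step at 0.025 has Φ(2.811 − 2.241) = 71.5% power at 258, before any gating on total fat. In a fixed sequence each depot keeps 0.05, but the first is reached and significant with probability between 0.803² = 64% (independent tests) and 80% (fully dependent tests). The second depends on both earlier steps.

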BMIz- BMI percentile and BMIz will be calculated based on the participant's age, height, and weight using the CDC 2000 growth charts.⁶¹ Severe obesity will be categorized as $\geq 120\%$ of the 95th BMI percentile.¹⁵

Waist circumference - will be measured at the natural waist (halfway between inferior border of rib cage and superior aspect of iliac crest) with clothing moved out of the way.

Body composition

DXA- Total body fat and trunk fat will be assessed by whole-body DXA using a GE iDXA scanner (GE Medical Systems, Milwaukee, WI) to quantify total and regional body fat (including trunk fat).

DXA Instructions given to participant: This scan measures the amount of bone, muscle, and fat in your body. The scan will be performed using a whole-body scanner. You will be required to wear a hospital gown, to remove all metal-containing objects from your body, and to lie down on the table. You will be carefully positioned on the table, and your legs will be placed together using two Velcro straps. A scanner emitting low energy X-rays and a detector will pass along your body. You will be asked to remain completely still while the scan is in progress. The scan takes approximately ten minutes.

MRI - Visceral fat, i.e. visceral adipose tissue, will be assessed by water-fat shifting MRI using the General Electric Discovery 750w 3.0 Tesla (GE Medical Systems, Milwaukee, WI). IDEAL-IQ imaging technique will be used to generate water-only, fat-only, in-phase, and out-of-phase echoes in a single acquisition with a 20-second breath-hold. For female subjects ages 12 and above or females under the age of 12 who are menstruating as verbally confirmed by a parent or legal guardian, a negative urine pregnancy test will be required prior to DXA or MRI scans.

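### Objective 2 splits continuous DXA fat change at an unstated percentile; its 80% power needs roughly equal groups and falls to about 68–73% at a quartile cut

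*Combined protocol and SAP*

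**What the plan says.** Under Body composition, the protocol measures the exposure on a continuous scale: "Total body fat and trunk fat will be assessed by whole-body DXA".

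Under Statistical Analysis, Objective 2, the main predictor is then formed from that measure: "Based on difference score between Years 0 and 2 for total body fat", "the group will be divided into two dichotomous groups using percentiles". The groups are called high fat gainers (HFG) and low fat gainers (LFG). Neither this section nor any other names the percentile or the intended group proportions.

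Under Power analysis, Objective 2, the target is worded as an association with fat gain itself: "The primary outcome for the second objective is the relationship between total fat accumulation and change in sedentary behavior". The calculation is nevertheless for the two groups: "we estimate an overall change in sedentary behavior of 12 minutes/day increase in the HFG and 3.6 minutes/day increase in the LFG". Table 6 gives this row an SD of 24, a minimum of 255 and a total of up to 345, and the text concludes that "this will provide at least 80% power for detecting a difference in the change between groups of 8.4 minutes/day".

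Ungrouped fat measures appear once in the Objective 2 analysis plan, in a later step: "Secondary analysis will use MRI and DXA as covariates in the model (namely the visceral, trunk, and total body fat"). LASSO and support vector machine methods then choose among them.

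**The concern.** There are two linked problems.

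- **The main exposure is not fully defined.** A median, tertile or quartile cut would all fit the text. The choice could be made after the data are seen, and it could change the result. The power statement depends on the choice but does not mention it.
- **Cutting a continuous measure discards information.** Children just either side of the cut are treated as different, and children far apart on the same side are treated as alike. Hypothesis 2 is about fat accumulation, so the split also tests something coarser than the hypothesis.

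At stake are a main Objective 2 test with less power than stated and less than the same data could give, and a cut-point left open to choice.

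**Working it through.** **Inputs.** From Table 6: difference 12 − 3.6 = 8.4 min/day, SD 24, stated minimum 255, up to 345 enrolled. From Anticipated Dropout: 25%, so 345 × 0.75 = 258.75, taken as 258 completers. Alpha 0.05 is stated for Objective 1 only; I assume the same, two-sided, here. The HFG:LFG ratio is not stated.

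**Step 1: reproduce Table 6.** For a smaller group of proportion p, the total needed is

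N = (1.960 + 0.842)² × 24² / [8.4² × p(1−p)] = 64.07 / [p(1−p)].

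- p = 1/2: 256.3, or 258 when rounded up to 129 per group. Stated: 255. Then 258/0.75 = 344, against up to 345.
- p = 1/3: 288.3, or about 385 enrolled.
- p = 1/4: 341.7, or about 456 enrolled.

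The other rows also match equal groups to within about 2% (198 against 194, 224 against 220, 298 against 292). A one-sided test would give 202 for the 8.4 row. So Table 6 implies roughly equal groups without saying so.

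**Step 2: power by cut at 258 completers, difference held at 8.4.** Power = Φ(0.35 × √[258 p(1−p)] − 1.960), where 0.35 = 8.4/24. For the median split: 0.35 × √64.5 = 2.81, and Φ(0.85) = 80.3%.

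**Step 3: power by cut with the slope held fixed.** Assume a normal exposure and a linear effect. A median split separates the group means by φ(0)/0.25 = 1.596 SD, so the slope that yields 8.4 is 8.4/1.596 = 5.26 min/day per SD. At another cut the difference becomes 5.26 × φ(z_p)/[p(1−p)], which widens as the cut moves outward. The within-group SD also rises very slightly.

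**Step 4: information kept by the split**, same assumptions: φ(z_p)²/[p(1−p)].

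| Split | Power, difference 8.4 | Difference, fixed slope | Power, fixed slope | Information kept |
|---|---|---|---|---|
| 50/50 | 80.3% | 8.40 | 80.3% | 63.7% |
| 40/60 | 78.6% | 8.47 | 79.3% | 62.2% |
| Thirds | 75.5% | 8.61 | 77.5% | 59.5% |
| Quartile | 68.2% | 8.92 | 73.2% | 53.9% |

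The t-test versions of the second column are 80.0%, 78.3%, 75.2% and 67.9%.

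**Step 5: the continuous alternative.** A within-group SD of 24 at a median split implies a residual variance of 576 − 5.26² × 0.363 = 565.9, so a residual SD of 23.79. The correlation is 5.26/√(565.9 + 27.7) = 0.216. Power at 258 is Φ(5.26 × √258/23.79 − 1.960) = Φ(1.59), about 94%; Fisher's z gives 93.9%. About 166 completers would give 80%.

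**Step 6: sensitivity to shape.** With a linear effect but other exposure distributions, the information lost by a median split is 25% (uniform), 48% (lognormal, sigma 0.5), 50% (Laplace) and 52% (exponential). The ranking of cuts also depends on shape: for that lognormal, an upper-quartile cut keeps 61% against 52% at the median.

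**The case against.** The strongest reply is that a high/low contrast suits the stated purpose. The protocol's problem description singles out children who gain fat quickly, and the Background calls for data that pick out those at high risk. A group difference in minutes per day is easy to read. Making the exposure continuous also changes the quantity that Table 6 was built on, so it is more than a change of wording. This stands as a reason to keep the contrast in the plan and to count the power rewrite as a cost. It does not justify leaving the cut unstated.

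The plan is also not silent on ungrouped fat. The secondary step includes visceral, trunk and total fat and compares imaging measures with BMIz. That is true, but there they are covariates competing under variable selection. It is not a prespecified, powered test of change in total fat.

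A reader might go further than the figures allow in two ways.

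- **That at least 36% of the information must be lost.** The 36% is 1 − 2/π and needs a normal exposure and a linear effect. The documents give neither a distribution nor a dose-response shape, and a uniform exposure would lose 25%.
- **That 80% power holds only at an exact median split.** By the z formula that reproduces Table 6, splits from about 46/54 to 54/46 keep 80%, and 40/60 gives 78.6%. By the t-test even 50/50 gives 79.97%, so the exact boundary has no practical meaning.

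**Conclusion.** The point holds in moderate form. The main Objective 2 exposure is a two-group cut of a continuous measure at an unnamed percentile, and the power statement is right only for roughly equal groups, with almost no slack. At a tertile cut power is about 75–78% and at a quartile cut about 68–73%. The ranges reflect whether the 8.4 min/day difference or the slope is held fixed.

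The cost of splitting at all is conditional. It is about 36% of the information at the median, and 80% against about 94% power, if fat change is normal and its effect linear. Across the other shapes examined, the median-split loss runs from 25% to about 50%.

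This does not show that Table 6 is miscalculated: for a median split its figures are sound on their own inputs. All powers here take its SD of 24 as given. Table 5 uses 69.6 for change in the same outcome under a different grouping, which is a separate question.

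**What to change.** In Statistical Analysis, Objective 2, make continuous Year 0 to Year 2 change in total body fat the primary exposure, reported per SD, with a spline term to check for non-linearity. In Power analysis, Objective 2, restate the power as a slope or correlation, giving the assumed distribution and SD. Keep HFG against LFG as a secondary descriptive contrast with the cut fixed at the median, and say that Table 6 applies to that contrast. If the sponsor prefers to keep the two-group test as primary, the minimum change is to state the percentile and the group proportions that Table 6 assumes.

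No new data, visits or participants are needed, and Objective 1 already models BMIz continuously before its own split. The costs are a linearity assumption, which the spline checks, and a rewritten power paragraph.
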